6.4. IMP compliance

The number of tablets dispensed and the number of tablets returned by the participant are to be counted by the investigator or a designated person from his/her team and recorded in the eCRF and therapeutic unit tracking form, or an equivalent document.

If the participant did not bring back all blisters dispensed at the previous visit, the investigator must estimate the number of IMP units taken by the participant since the previous visit, by questioning him/her.

IMP compliance will be assessed at visits W4, W8 and W12. It will be evaluated by the method described above.

6.5. Discontinuation of the IMP

After the discontinuation of the IMP, the participants' treatment is left to the physician's discretion. Further patient treatment after the discontinuation of the IMP will be conducted according to the Standards of specialized diabetes care approved in Russia [14].

7. ASSESSMENT OF EFFICACY

7.1. Efficacy measurements

Efficacy measurements performed during the study are indicated in Table 1.

Criteria for evaluation:

Primary evaluation variable:

- HbA1c (The change from baseline in HbA1c to Week 12)

Secondary evaluation variables:

- change in fasting plasma glucose
- change in postprandial plasma glucose (2-hours after meal)
- change body weight
- change in waist circumference

Exploratory: ratio of patients at target (HbA1c < 7% & HbA1c <6.5% at week 12), 24 hours excreted urinary glucose (quantitative), pharmacokinetic and pharmacodynamic parameters of luseogliflozin in the subjects in PK/PD subset.

7.2. Methods and measurement times

The study visits should be performed in the morning in fasting conditions before IMP intake on the day of the visit. IMP intake on the day of the Week 4 and W8 visits should be done from a new pack allocated using IRS at the visit.

HbAlc at central laboratory will be measured at selection, inclusion, W 8 and Week 12 visit. Fasting plasma glucose, body weight and waist circumference are to be measured at each study visit. Waist circumference will be measured at midway between the lowest ribs and the iliac crest in the standing position at the end of normal expiration, the tape should be in horizontal plane.

Before the start of the treatment (W0) and the end of the double-blind treatment (W12) blood will be collected 2 hours after the start of the standardized meal, and plasma glucose will be measured. A standardized meal (breakfast) containing energy about 600 kcal will provided. At W12 visit the IMP should be taken during the visit before standardized breakfast.

Regarding the PK assessment, in the subset of patients the sampling should be performed at Week 4 visit; 12 samples per patients are planned. Sampling times are as follows: T0 (before administration); 0.25 (15 min); 0.5 (30 min); 1; 1.5; 2; 3; 4; 6; 8; 12 and 24 hours after administration. In this subset of patients the 24-hour urinary glucose excretion will be measured at Week 0 and Week 4 visits as well. The diet, fluid intake and physical activity during the days of 24-hour urine collection at W0 and W4 should be similar as far as possible. The detailed instructions regarding the food, fluid, physical activity etc. related to 24-hour urine collection and the conditions for blood sampling will be described in the Investigator's Guide for PK/PD.

At visits, the proper timing of both drug intake and of blood sampling should be collected.

8. SAFETY MEASUREMENTS

All adverse events and other situations relevant to the safety of the participants must be followed up and fully and precisely documented in order to ensure that the sponsor has the necessary information to continuously assess the benefit-risk balance of the clinical trial.

8.1. Specification of safety parameters

Safety measurements performed during the study are indicated in Table 1. This includes:

- Physical examination,
- Vital signs (HR, systolic and diastolic BP)
- 12-lead ECG
- Laboratory parameters (haematology, biochemistry, urine analysis, ketones),
- Adverse events recording (including AE of special interest).

8.2. Methods and measurement times

8.2.1. Physical examination

Physical examination will be carried out at each study visit and must be documented in the source documents. Any clinically significant abnormalities during the study should be recorded as an adverse event.

8.2.2. Vital signs

HR and BP will be measured at all visits after at least 5 min rest. BP should be assessed in the sitting position using 2 measurements taken at least 2 minute intervals, preferably with an automatic blood pressure device. Blood pressure should be measured at the same arm and using the same device, throughout the study as far as possible. Both measurements should be reported in the e-CRF and the mean value will be automatically calculated.

Uncontrolled hypertension is defined as a mean of 2 measurements for systolic blood pressure >180 mmHg and/or for mean diastolic blood pressure >100 mmHg. The criteria will be rechecked at inclusion; if the values are over these limits, the patient must not be included.

8.2.3. Standard electrocardiogram

A standard electrocardiogram (12-lead) will be performed at selection visit and Week 12. The ECG will be performed after 10 minutes at rest with patient in supine position. The interpretation of the ECG trace should be done by a qualified medical doctor associated with the centre.

The ECG traces should be kept in the patient's file for source documentation.

8.2.4. Blood glucose monitoring

Fasting blood glucose will be measured at selection, inclusion, Week 4, Week 8 and Week 12 in a local laboratory. In addition, during the study the patients will perform SMBG at home using a glucose meter and the test strips provided for the study:

- Selection period: One measurement every day in a fasting state before breakfast.
- After inclusion (during double-blind treatment period and until Week 14): One measurement every day in a fasting state before breakfast and 4 measurements during a day (including preprandial and postprandial state) once a week

SMBG can be performed more frequently, if necessary, according to investigator's judgement. The patient will record information in the study diary provided by the investigator at the visits. Patients experiencing symptoms of hypoglycaemia will also perform a blood glucose self-measurement at the time of the event.

The patients should be instructed to contact the investigator:

- If they record blood glucose levels equal or less than 3.9 mmol/L (70 mg/dL) at any time during the study. The investigator will determine whether the patient should return to the site for further assessment. In addition, the patient should be instructed on recognition of the symptoms of hypoglycaemia and requested to measure glucose by glucose meter when they experience these symptoms.
- If, between Inclusion and Week 4 the fasting glucose is equal or above 240 mg/d (13.3 mmol/l), and between Week 4 and Week 12 is equal or above 220 mg/gl (12.2

mmol/l) the investigator should make every effort to have the patient visit to the clinic for a fasting plasma glucose measurement as soon as possible but within 7 days as maximum.

Glucometer readings should be printed out at each study visit and kept in the patient's medical file.

The measurements of SMBG will not be recorded in the e-CRF, except in case of AE reporting.

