6.3.1. Rescue treatment for loss of glucose control

The patients with loss of glucose control according to the following criteria will be prescribed rescue treatment during the double blind period of the study and will be allowed to remain in the study:

- Week 1-4: glucose level at SMBG or at the visit 240-270 mg/dl (13.3-15.0 mmol/l) inclusive after overnight fast or >400 mg/dl (>22.2 mmol/l) in a randomly performed measurement
- Week 4-12: glucose level at SMBG or at the visit 220-270 mg/dl (12.2-15.0 mmol/l) inclusive after overnight fast or >400 mg/dl (>22.2 mmol/l) in a randomly performed measurement

Insulin therapy may be instituted as needed. Alternatively, at the discretion of the Investigator, other antidiabetic medication can be prescribed; SGLT 2 inhibitors are not allowed as rescue therapy.

A complete final evaluation should be made before initiation of rescue therapy, if possible. Information to be collected should be as at Week 12 visit as indicated in Table 1 5.7.2

The details of rescue medications should be recorded in the e-CRF.

In case of hypoglycaemia that may put the patient on risk (e.g. repeated symptomatic hypoglycaemia or major hypoglycaemia), appropriate dose adjustment of antidiabetic therapy such as dose reduction/discontinuation of ongoing rescue medication or existing background therapy should be imitated. Reduction or discontinuation of ongoing rescue medication should be considered before a reduction in the dose of existing background therapy.

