When an event is reported to a site, the site staff should inquire regarding the symptoms experienced, SMBG obtained at time of event, and whether confounding factors (e.g., increased physical activity, intercurrent illness, new concomitant treatment, skipped meal, etc.) contributed to the event. In the presence of such confounding factors, the Investigator should advise the patient on how to avoid similar episodes in the future. In the absence of confounding factors, the dose of metformin may be decreased at the Investigator's discretion.

The confirmed or asymptomatic hypoglycaemia episodes, and symptoms suggestive of hypoglycaemia will be reported by the investigator in the e-CRF according to the general instructions for completion.

Major hypoglycaemia events should be reported as SAE.

Polyuria, pollakiuria

Events related to decreased fluid volume (including dehydration and BP decrease)

Polyuria or pollakiuria may occur due to the diuretic action of luseogliflozin.

Reduction of body fluid volume may occur.

Patients should be monitored sufficiently. Attention should be paid to the events related to decreased fluid volume.

When abnormalities including dehydration and decrease in blood pressure occur, appropriate measures should be taken, especially in patients who are likely to have hypovolemia (including elderly patients and patients with combined use of diuretics). Appropriate additional investigations will be performed as required. Management of the event, including fluid replacement and IMP interruption, will be based on the Investigator's clinical judgement.

The site staff should collect and document information on the timing of onset, concomitant drugs and other aspects of the event.

Ketoacidosis

Due to the mechanism of action of luseogliflozin, i.e., enhancement of urinary glucose excretion, fatty acid metabolism may be enhanced, which may lead to ketosis and ultimately ketoacidosis, even when plasma glucose is well controlled. Marked increase in blood glucose levels may be not observed.

Nausea/vomiting, decreased appetite, abdominal pain, severe thirst, malaise, dyspnea or disturbance of consciousness may be suggestive of ketoacidosis.

Appropriate ketone tests should be performed as required. Management of the event, including discontinuation of the IMP, will be based on the Investigator's clinical judgement.

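### The patient contact list in 8.2.4 omits one of the rescue triggers in 6.3.1: a random glucose above 400 mg/dl

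*Protocol*

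**What the plan says.** **Rescue criteria (Protocol 6.3.1).** In each of two periods a patient qualifies for rescue in either of two ways. The first is a fasting range, which up to Week 4 reads "glucose level at SMBG or at the visit 240-270 mg/dl (13.3-15.0 mmol/l) inclusive after overnight fast"; from Week 4 to Week 12 the lower end falls to 220 mg/dl. The second is the same in both periods: ">400 mg/dl (>22.2 mmol/l) in a randomly performed measurement". The opening words of each criterion name self-monitoring (SMBG) or a visit measurement as the source.

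**Home monitoring and patient contact (Protocol 8.2.4).** After inclusion, patients take one fasting reading every day and, in addition, "4 measurements during a day (including preprandial and postprandial state) once a week". They are to contact the investigator in two situations:

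- Low values: "If they record blood glucose levels equal or less than 3.9 mmol/L (70 mg/dL) at any time during the study".
- High fasting values. The limit for the first period reads "If, between Inclusion and Week 4 the fasting glucose is equal or above 240 mg/d (13.3 mmol/l". For the second period, up to Week 12, the limit drops to 220 mg/dl (12.2 mmol/l). In both cases the investigator is to try to bring the patient in for a fasting plasma glucose measurement within 7 days at most.

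The planned review of all other home readings is at visits: "Glucometer readings should be printed out at each study visit". The same section says that SMBG values do not enter the e-CRF unless an adverse event is reported.

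**The concern.** The high-glucose part of the contact list has the same fasting lower limits as 6.3.1 and changes them at the same visit. It looks meant to bring home readings that meet the rescue criteria to the investigator's attention. The random-reading trigger was not carried over.

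A patient who follows 8.2.4 to the letter can therefore record a value that meets a rescue criterion and have no instruction to tell anyone. What is at stake is patient safety between visits, and even application of 6.3.1: whether the random trigger is acted on promptly would depend on the habits of the patient or site. Because SMBG values are generally kept out of the e-CRF, a trigger that was met but not reported would be visible only in the diary and the glucometer print-outs at the site.

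**Working it through.** **Step 1. Units.** Dividing mg/dl by 18.016 reproduces the protocol's mmol/l figures, so the two sections can be compared directly:

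| mg/dl | Protocol, mmol/l | Recomputed |
|---|---|---|
| 70 | 3.9 | 3.89 |
| 220 | 12.2 | 12.21 |
| 240 | 13.3 | 13.32 |
| 270 | 15.0 | 14.99 |
| 400 | 22.2 | 22.20 |

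**Step 2. Match each rescue trigger to a contact rule.**

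| Trigger in 6.3.1 | Accepted from SMBG | Contact rule in 8.2.4 |
|---|---|---|
| Fasting 240–270 mg/dl, to Week 4 | Yes | Yes: fasting, 240 or above |
| Fasting 220–270 mg/dl, Week 4 to 12 | Yes | Yes: fasting, 220 or above |
| Random above 400 mg/dl, to Week 4 | Yes | None |
| Random above 400 mg/dl, Week 4 to 12 | Yes | None |

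The fasting contact rule has no upper end, so it covers the whole fasting rescue range. The uncovered case is a non-fasting reading above 400 mg/dl.

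**Step 3. Can such a reading arise at home?** Yes. The weekly four-reading day includes readings after meals, and 8.2.4 allows more frequent SMBG if the investigator judges it necessary.

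**Step 4. Longest wait for the planned review.** The visits are nominally 28 days apart, and W4, W8 and W12 each have a window of ±3 days (Protocol Table 1).

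- W0 to W4: 28 + 3 = 31 days.
- W4 to W8: (56 + 3) − (28 − 3) = 59 − 25 = 34 days.
- W8 to W12: (84 + 3) − (56 − 3) = 87 − 53 = 34 days.

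Rescue under 6.3.1 applies to the double-blind period, so the W12 to W14 interval is not counted.

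**Step 5. What the worst case requires.** The reading must fall right at the start of the interval, the visits must sit at the extremes of their windows, and no later fasting reading may reach the call-in limit. With one fasting reading each morning, that means 31 − 1 = 30 or 34 − 1 = 33 consecutive mornings below 240 or 220 mg/dl before the visit day. The protocol gives no data on how often this would follow a random value above 400 mg/dl, so no frequency can be stated.

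**The case against.** The strongest counter-argument is that daily fasting SMBG acts as a backstop. A patient with a random value above 400 mg/dl may well have a fasting value above the call-in limit soon afterwards, and that already requires contact. Nothing forbids an earlier call, and 8.9.2 foresees telephone contact as a way for the investigator to learn of events. This stands. It makes the full 31 or 34 days a worst case, and it rules out saying that there is no route to the investigator before the next print-out. It does not remove the mismatch: 6.3.1 makes the random reading a trigger in its own right, without a confirming fasting value.

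A reader might infer more than the documents support, in three ways.

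- **That the contact rules fail to detect ketoacidosis.** Section 8.6 warns of ketoacidosis with well-controlled glucose ("Marked increase in blood glucose levels may be not observed"), and the contact rules are based on glucose. But 8.2.4 is a glucose-monitoring section, and no text gives it the task of detecting ketoacidosis. Section 8.6 provides for ketone tests as needed. Under 8.2.5, scheduled testing includes urine ketones as well as blood strips. What patients are told about symptoms may be in the participant information form or the diary, neither of which is shown.
- **That ketoacidosis ranks above the other adverse events of special interest.** Section 8.6 lists them without ranking.
- **That late rescue biases the primary analysis.** The primary analysis imputes data collected after rescue, so the rescue date does decide which W8 and W12 HbA1c values are kept. But later rescue may simply let a value be observed before rescue instead of being imputed, which suits the stated aim of an effect without rescue. No direction or size of bias can be shown.

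**Conclusion.** The point holds as a mismatch between two stated rules. Section 6.3.1 accepts a home random reading above 400 mg/dl as a reason for rescue, and 8.2.4 schedules readings that could show one, but the contact list does not include it. Such a reading can go unreported until the next visit; it does not follow that it will.

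The delay is at most 31 days before W4 and 34 days in each of the two later intervals, subject to the conditions in step 5. This rests on reading the SMBG source in 6.3.1 as applying to both parts of each criterion, which is how the sentence is built, and on the patient doing no more than 8.2.4 asks.

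It is more than missing detail, because it bears on patient safety and is easily corrected. It does not undermine the design, and no effect on the primary result is shown.

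**What to change.** Reconcile the contact list in 8.2.4, and the matching diary instructions, with 6.3.1, so that every SMBG value the protocol already treats as a rescue trigger is also one the patient is told to report. The wording, timing and handling of such a report are for the sponsor to decide. No new threshold and no change in care is proposed.

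The cost is a line of text in the protocol and the diary, and a few extra patient calls.

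As a side check, the sponsor should confirm that the patient instructions as a whole, including the information form, are consistent with the warning in 8.6 that ketoacidosis may occur without high glucose.

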8.2.5. Laboratory assessments

The blood and urine samples will be assayed by a local laboratory (except HbAc1 measurements and urinary glucose, which will be done at central laboratory). Blood ketones will be assessed using test strips during the visit.

The blood tests must be obtained under fasting conditions (i.e., after the patient has fasted for ≥ 10 hours). Fasting is defined as nothing ingested by mouth except water (and any essential medications). If a patient is not fasting, the Investigator will reschedule the blood sampling within the visit timeframe window previously defined. Laboratory certification (including expiration date) and normal reference ranges for all required parameters used during the study will be enclosed in file with the Sponsor prior to study initiation. Local laboratory normal ranges values will be collected, as well as any update in these values during the study and must be documented on the corresponding page of the e-CRF.

Outside of normal range values should be assessed by the Investigator. The Investigator will exercise medical and scientific judgment in deciding whether an abnormal laboratory finding or other abnormal assessment is clinically significant.

The following parameters must be evaluated:

- Haematology: white cell count with differential formula (neutrophils, lymphocytes, monocytes, eosinophils, and basophils), red cell count, hemoglobin, hematocrit, and platelets count,
- Biochemistry: creatinine, eGFR (according to MDRD formula), total bilirubin, ALT, AST, total protein, sodium, potassium, chloride, total cholesterol, LDL cholesterol, HDL cholesterol, triglycerides, uric acid,
 - eGFR will be calculated in e-CRF using the MDRD formula (Modification of Diet in Renal Disease Study equation) (Levey, 2006): eGFR (mL/min/1.73 m2) = 175 × (serum creatinine in mg/dL) $^{-1.154}$ × (age in years) $^{-0.203}$ × (0.742 if female)
- Blood ketones using test strips
- Urine analysis: color, appearance, specific gravity, pH, protein, ketones, bilirubin, erythrocytes, leucocytes, nitrite, microscopic examination.

Haematology and biochemistry tests are to be performed at selection period and at W12 visit, blood ketones— at W0 and at every study visit including W14 visit, urine analysis — at selection period and at every study visit including W14. Abridged laboratory test (hematocrit; total bilirubin, ALT, AST, creatinine, eGFR, serum sodium, potassium, chloride) will be performed at W 4 and W8 visits.

8.3. Definition of Adverse events

An adverse event (AE) is defined as any untoward medical occurrence in a patient or clinical investigation subject administered a pharmaceutical product and which does not necessarily have a causal relationship with this treatment. An adverse event can therefore be any unfavourable and unintended sign (including an abnormal laboratory finding), symptom, or disease temporally associated with the use of a medicinal product, whether or not related to the medicinal product (*GCP EAEU*).

During and following a subject's participation in a trial, the investigator/institution should ensure that adequate medical care is provided to a subject for any adverse events, including clinically significant laboratory values, related to the trial. Adverse events and/or laboratory abnormalities identified in the protocol as critical to safety evaluations should be reported to the sponsor according to the reporting requirements and within the time periods specified by the sponsor in the protocol (*GCP EAEU*).

Considering that study participants are patients, who may have different disorders and diseases in medical history, and that laboratory, ECG and vital signs abnormalities will be included in the safety analysis in addition to AE, an AE should be registered by the Investigator in case of:

- any unfavourable and unintended sign (including an abnormal finding from an additional examination such as lab tests, ECG,...) which is deemed clinically relevant by the investigator,
- any symptom or disease,
- any worsening during the study of a symptom or a disease already present when the participant entered the study (increase in frequency and/or intensity), including the studied pathology,

and detected during a study visit or at an additional examination or occurred since the previous study visit (including relevant event reported in participant's diary).

Of note:

- Any hospitalisation for PK sampling in the study, social reasons, educational purpose (e.g. learning of diabetes management by the participant) or routine check-up should not be considered as an adverse event and should not be reported in the e-CRF.
- The following procedures, whether planned before the study or not, whether leading to a hospitalisation or not, should be reported in the specific page "Procedures not subsequent to an adverse event" of the e-CRF:
 - therapeutic procedures related to a non-aggravated medical history (e.g. cataract extraction not due to an aggravation of the cataract during the study, haemodialysis sessions related to a renal insufficiency not aggravated during the study),
 - prophylactic procedures (e.g. sterilisation, wisdom teeth removal),
 - comfort procedures (e.g. cosmetic surgery),
 - control procedures of a pre-existing condition without aggravation (e.g. colonoscopy to control the remission of colon cancer).

